6.7 Study logistics

The Novartis Pharma GmbH field employees involved will be trained in the regulatory framework parameters, the FSA Code of Conduct and the recommendations of BfArM/PEI and the VFA.

The study documents will be distributed by the field employees. No advertising for the drug under investigation in this NIS that has any temporal or substantive link to the study-related activities of the field employee is permitted. The physician must be free to decide whether to participate; no attempt must be made to influence this decision in any way. The drug is prescribed exclusively on the basis of therapeutic need, a decision for which the physician has responsibility.

The documentation of follow-up examinations is to be carried out by the physician in electronic form only via the internet in the electronic Case Report Form (eCRF).

6.8 Remuneration

Remuneration for giving the patient information, complete documentation and the immediate notification of any serious adverse events (no later than 24 hours of their becoming known) will be made based on an assessment of services.

The average remuneration of EUR 850.00 per completely documented observation of a patient for the average observational period of 10 months is constituted as follows:

•	Documentation of the start of observation	€ 150.00
•	Observation at week 2	€ 100.00
•	Observations at month 1, 3, 6, 9etc.	€ 125.00
•	Documentation of the end of observation (one occasion)	€ 100.00
	Description of pressures on death following discontinuation of the theorem	

 Documentation of progress or death following discontinuation of the therapy with Afinitor[®] and exemestane (every six month until progress / death € 110.00

At 5% of the participating sites, on-site monitoring will be conducted in compliance with the applicable data protection provisions to ensure the confidentiality of patients' personal data. Remuneration for this on-site monitoring, if conducted, will consist of an additional \in 150.00. This payment covers preparations and follow-up for the monitoring visit and availability during monitoring.

Separate remuneration of \in 75.00 per fully completed questionnaire will be paid for the additional time involved in filling out the questionnaires that may be required for the risk management plan (as amended).

7 Adverse Events

7.1 Definition

The term "adverse event" (AE) describes any adverse or unintended manifestation (e.g. abnormal laboratory finding), symptom, or any illness **coinciding with** the use of a Novartis drug or **the drug(s) studied in this NIS**, regardless of whether a causal relationship with this drug is suspected. The drug studied in this NIS means the drug that is the subject of this study and includes combination or comparator products if they have been specified as part of the study aims. **The drugs in this BRAWO study are Afinitor**[®] and exemestane. Adverse events that occur after the time of **the initial administration of** Afinitor[®] and exemestane are recorded in the BRAWO NIS. Medical conditions or diseases that were already present before the initial administration of Afinitor[®] and exemestane the initial administration of Afinitor[®] and exemestane worse after starting treatment with Afinitor[®] and exemestane.

In addition, all the events or situations listed below are considered adverse events, regardless of whether or not a clinical symptom occurred:

• Interaction between drugs and/or between the drug(s) and food, with or without clinical

symptoms

- Exposure to drugs during pregnancy or lactation (irrespective of the outcome)
- No efficacy or inadequate efficacy of a compound after exhausting the recommended dose range, with or without clinical symptoms
- Accidental or deliberate overdose, with or without clinical symptoms
- Drug abuse and drug misuse, dependence
- Withdrawal/discontinuation/rebound phenomenon, with or without symptoms in each case
- **Medication and administration errors**, i.e. incorrect or accidental administration or delivery, including taking another person's medication, , or confusion of names (e.g. Lamisil mistaken for Lamictal), with or without symptoms in each case
- **Progression** or **deterioration of the underlying disease** with a suspected causal relationship, see Section 7.8
- (Unexpected) positive effects
- Occupational / accidental exposure
- Quality defects

Adverse events are classified as serious (SAE, see 7.2) or non-serious adverse events (NSAE, see 7.4).

All adverse events that occur are to be documented according to the type of event, first occurrence, duration and intensity in the patient observation form (eCRF). In addition, it must be documented whether a causal relationship has been seen, and if so, with what drug (see 7.5). Countermeasures initiated (e.g. pharmacological treatment, dose adjustment/ discontinuation/pause of medication), relevant concomitant medication, relevant investigation and laboratory findings and the outcome of the adverse event must also be reported.

Please ensure that the events are entered in full in the report form (eCRF) from the point of view of clear categorisation (e.g. pre-existing diseases, adverse event observed) and evaluation (e.g. causality) from the perspective of the reporting physician/medical professionals. Adverse events should be documented by a physician or other medical professional involved in the case (e.g. nurse, dentist, pharmacist), but must always be confirmed by the treating physician or the physician participating in the NIS. Hospital discharge reports, other findings and laboratory results should be sent only if requested by Novartis. Please note that **conscientious and fully completed documentation** facilitates quick, accurate data capture and, if necessary, reporting and **allows follow-up requests to be** avoided.

The incidence and profile of AEs occurring during the observational period are evaluated based on the currently applicable MedDRA version-coded reported events (System Organ Class [SOC] and Preferred Term [PT]).

Adverse events (SAEs and NSAEs) are recorded irrespective of the causal relationship up

to 30 days after the end of treatment with Afinitor[®] and exemestane within this NIS and processed according to the procedures described below. Adverse events with a suspected causal relationship with Afinitor[®] in the BRAWO NIS can be documented after this period.

All AEs and SAEs with causal connection to Afinitor[®] and exemestane of patients who stopped therapy with Afinitor and exemestane prior to disease progression and who entered PFS follow up period have to be documented in eCRF and reported starting day 31 after stopping treatment until day 30 after last visit (please refer to section 7.2 and 7.3). Occurrence of death have to be documented in eCRF and reported as SAEs independently from causal connection from day 31 after stopping treatment with Afinitor[®] and exemestane until day 30 after last visit (please refer to section 7.2 and 7.3).

After the end of the observation period specified for the BRAWO NIS (end of the observation period) in the observation plan in Section 6.3, reported adverse events (SAEs and NSAEs) must be included in this NIS irrespective of the causal relationship up to 30 days after the end of the observation period and processed according to the procedures described. After these 30 days, all adverse events (SAEs and NSAEs) subsequently reported to CRO

will be forwarded to Novartis outside this NIS, i.e. not included in the study.

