If the treatment with Afinitor[®] and exemestane is stopped prior to disease progression, the following data will be collected approximately every six month until progression or death of the patient:

- Follow up treatment
- Date of progression (if applicable)
- AEs and SAEs with causal connection to Afinitor[®] or exemestane / occurrence of death independent from causal connection (see below) starting day 31 after stopping combination therapy until day 30 after last documentation in the context of PFS follow up visit (last contact

of patient to study centre). All AEs and SAEs with causal connection to Afinitor or exemestane will be documented – inclusive progression with causal connection.

Occurrence of death will be documented independently from causal connection of the combination therapy (Afinitor[®] and exemestane) from day 31 after stopping combination therapy until day 30 after last documentation in the context of PFS follow up visit (last contact of patient to study centre).

Statistical methods:

The NIS will be analyzed using epidemiological methods under primary use of descriptive statistical methods.

Ethical requirements and regulations:

The NIS will be conducted in compliance with the FSA Code of Conduct (dated 07/05/2008, Federal Gazette No. 68, p. 1636) and in accordance with the recommendations of the Federal Institute for Drugs and Medical Devices (BfArM) and the Paul Ehrlich Institute (PEI) on the planning, implementation and evaluation of observational studies dated 07/07/2010 and the VFA recommendations for improving the quality and transparency of non-interventional studies dated 31/01/2007 and 23/04/2007.

Timetable:

The study will be conducted between October 2012 and December 2017.

4 Introduction and rationale

Breast cancer is the **most common cancer** in women. In Europe, breast cancer accounts for approximately 13% of all newly diagnosed cancers and causes approximately 130,000 deaths a year (Boyle et al. 2005).

Approximately 40% of newly diagnosed breast cancer patients develop **metastatic disease**. The treatment of metastatic breast cancer is palliative in nature and focuses on the reduction of tumour size, slowing disease progression and reducing the complications associated with the disease and treatment such as fatigue, bone fractures and hypercalcaemia. The average life expectancy for women with metastatic breast cancer is usually 24 to 30 months (World Health Organization Facts and Figures).

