6.4 Observation parameters

In this non-interventional study, diagnostic measures and medically indicated examinations are documented only if they were conducted in accordance with normal routine practice. The points described under 6.4.1 to 6.4.3 are guideline observation parameters and are solely for the purpose of orientation.

Optional intermediate examinations can be anticipated per patient corresponding to routine practice in normal conditions. Findings are to be documented at the time of inclusion and after approx. 2 weeks, 1, 3, 6, 9, 12... etc. months until the end of treatment with Afinitor[®] and exemestane or until the end of the observation phase, whichever occurs first.

To assess quality of life and physical activity before the start of treatment and during treatment, questionnaires in hard copy will be provided. To estimate patient compliance, patients will be given calendar overviews.

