6.4.4 End of observation

The documentation of the end of treatment with Afinitor[®] is not bound to the target observation interval (e.g. after month 1, 3, 6 etc.), but should be carried out at the soonest possible time that is

in line with medical practice. The following observation parameters will be recorded:

- Reasons for the end of documentation (withdrawal of consent, lost to follow-up, death, discontinuation of treatment with Afinitor[®])
- Date, dosage and pharmaceutical form of the last administration of Afinitor®
- Reason for ending treatment (lack of efficacy, disease progression, intolerability, poor compliance)
- Evaluation of response to treatment (from imaging and/or clinical assessment of status in accordance with routine practice)
- Follow-up treatment
- Documentation of adverse events

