7.2 Serious Adverse Events

- are fatal,
- are life-threatening¹,
- require or prolong hospitalisation,
- lead to inability to work, persistent or severe disability or incapacity³,
- result in a congenital anomaly or birth defect,
- are medically significant⁴.

1 Refers to an adverse event that carries a fatal risk for the patient at the time of the reaction. It does not refer to a reaction that could hypothetically result in death if it developed to a higher level of severity or complications.

2 This refers to inability to work as a result of permanent damage to health

3 Disability is considerable incapacity or permanent damage

4 Medically significant adverse events (AEs) are AEs that are not immediately fatal or life threatening or necessitate hospitalisation, but can considerably impair the patient. AEs are also medically significant if they require intervention/treatment to prevent a condition corresponding to the criteria for the definition of an SAE.

Inpatient treatment is not considered to be a serious adverse event if one of the following points applies:

a) Hospitalisation, that is part of the standard of care or surveillance of the disease investigated in the NIS and that is not due to worsening of the disease

- b) Elective admission or hospitalisation, that was already planned before inclusion in the NIS for the treatment of pre-existing diseases without relation to the disease investigated in the NIS and without deterioration since application of the drugs studied in this NIS
- c) Hospitalisation for social reasons and for short-term care without deterioration of the patient's general condition or the disease investigated in this study.

The decision as to whether an event constitutes an SAE depends only on whether one of the formal criteria named above is present and is *independent of the assessment of whether there is a causal relationship between taking a drug and the occurrence of the SAE*.

Reporting periods for SAEs

All serious adverse events are to be documented fully in the electronic case report form (eCRF) under the "Adverse Events" tab and submitted in the system within 24 hours of becoming known. Exception: In the event that entering an SAE in the eCRF is impossible for technical or other reasons, the SAE report can also be faxed as a hard copy "SAE report" directly to **Exception**.

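### All-cause adverse events are to be recorded to day 30 after treatment, but no scheduled entry asks about days 1–30

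*Protocol*

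**What the plan says.** **The reporting rule.** Section 7.1 reads "Adverse events (SAEs and NSAEs) are recorded irrespective of the causal relationship up" and continues "to 30 days after the end of treatment with Afinitor[®] and exemestane within this NIS". Sections 7.2 and 7.3 set the route: SAEs go into the eCRF within 24 hours, and non-serious AEs within 10 days. Both clocks start when the event becomes known. A fatal event is an SAE.

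**The schedule.** Section 6.4 has findings documented at inclusion, at about two weeks and then at 1, 3, 6, 9, 12 and further "months until the end of treatment with Afinitor[®] and exemestane or until the end of the observation phase, whichever occurs first". Section 6.4.4 frees the end-of-treatment record from the visit interval, "but should be carried out at the soonest possible time that is" consistent with medical practice. It includes an AE item and names discontinuation of Afinitor among the reasons for ending documentation. In the scheme in section 3, the last AE/SAE column is the end of treatment.

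**PFS follow-up.** This applies only to patients who stop before progression, with data collected about every six months. Section 3 has causally related AEs, and deaths of any cause, documented "starting day 31 after stopping combination therapy until day 30 after last documentation in the context of PFS follow up visit". Section 7.1 gives the same start for related AEs, "reported starting day 31 after stopping treatment until day 30 after last visit", and for deaths, "independently from causal connection from day 31 after stopping treatment with Afinitor[®] and exemestane until day 30 after last visit". Section 6.4.5 lists date of progression or death, related AEs and any death, without a day-31 limit.

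**The concern.** The rule runs 30 days longer than the schedule that serves it. A site working from 6.4, 6.4.4 and the scheme makes its last AE entry at discontinuation and may regard the patient as closed. A site working from 7.1 keeps collecting for 30 days. No sentence in the protocol connects the two.

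Treatment often ends because of progression or intolerability (both are listed reasons in 6.4.4), so the following weeks are not a period in which few events can be taken for granted. If AEs there are found less completely than AEs on treatment, the incidences and incidence densities in section 12.2 mix two levels of ascertainment. Section 13 classifies the study as a post-authorisation safety study, so completeness of AE data is a main output.

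**Working it through.** The protocol gives no figure of its own for this window, so there is none to reproduce. The check has two parts: rule against schedule, then the size of the window.

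**1. Is any day uncovered by rule?** All-cause AEs and SAEs: days 1–30 (7.1). Related AEs and all deaths, for patients in PFS follow-up: day 31 onward (section 3 and 7.1). The two windows adjoin: 0 days uncovered, 0 days overlapping.

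**2. Does any scheduled entry ask about days 1–30?**

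| Patient | Last AE entry in the schedule | Next scheduled entry | What that entry collects |
|---|---|---|---|
| Stopped at progression | End of treatment, made promptly | None | – |
| Stopped before progression | End of treatment, made promptly | PFS follow-up, about 6 months later | Date of progression or death, any death, causally related AEs |

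On the first path, nothing asks about the window after the end-of-treatment entry. On the second, a death in days 1–30 is picked up through the date of death, but an AE judged unrelated is not asked for.

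**3. Size of the window.** Inputs: about 3000 patients (6.1) and an average observation period of 10 months (6.8), taken here as time on treatment.
- Window, if every patient contributes all 30 days: 3000 × 30 / 365.25 = 246 person-years.
- Observation: 3000 × 10 / 12 = 2500 person-years.
- Share: 246 / (2500 + 246) = 9.0%.

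The 246 is a maximum, because patients who die on treatment, or are still on treatment when observation ends, contribute less or nothing.

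**4. What incomplete reporting could do.** The documents give neither a reporting rate nor an event rate for the window, so both are assumed. Let r be the event rate in the window relative to the earlier rate and c the share of its events reported. With 10 months = 304.4 days:

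share of all events missed = (1 − c) × 30r / (304.4 + 30r)

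| | r = 0.5 | r = 1 | r = 2 |
|---|---|---|---|
| c = 1 | 0% | 0% | 0% |
| c = 0.5 | 2.3% | 4.5% | 8.2% |
| c = 0 | 4.7% | 9.0% | 16.5% |

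In the extreme case where person-time runs to day 30 and no event in the window is recorded, the incidence density falls to 10 / (10 + 30/30.44) = 0.91 of the on-treatment value.

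**5. Deaths expected in the window.** Section 4 gives an average life expectancy of 24 to 30 months in metastatic disease. Reading this as a median with constant hazard, the probability of death in 30 days (0.986 months) is 1 − exp(−0.986 × ln 2 / m). That is 2.8% for m = 24 and 2.3% for m = 30, or about 84 and 68 of 3000 patients. These are deaths expected in any 30 days under those assumptions, not deaths missed.

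**The case against.** The strongest reply is that 6.4 times routine findings while section 7 governs AE reporting, so the two do different jobs and do not conflict. AE capture is event-driven and does not depend on a visit. Nothing says that AE entry closes with the end-of-treatment record; section 7.1 allows suspected related AEs to be documented even after day 30. Section 10.2 adds checks of free text and queries for undocumented AEs, and section 11 includes SAEs and non-serious AEs in source data verification. In a non-interventional study, reporting when an event becomes known is a natural design.

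Much of this stands. A reader might infer from the schedule and the day-31 start that no record covers days 1–30, that events and deaths there are under-counted, or that 68 to 84 deaths would go unrecorded. The documents support none of these. Days 1–30 lie inside the study by the wording of 7.1, a death in them is a reportable SAE, and 6.4.5 collects date of death without a day-31 limit. Nor does section 12.2 say where person-time ends, so the factor 0.91 is a bound and not a prediction.

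What the reply does not remove is that the reporting clocks govern how fast a known event is reported, not whether anyone looks for it. On-site monitoring covers 5% of sites (6.8), and free-text checks can find only what was entered. The remark in 6.4 that the parameters are for orientation applies to 6.4.1 to 6.4.3, not to 6.4.4.

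**Conclusion.** The point holds as a mismatch between rule and schedule. Section 7.1 requires all-cause AE recording to day 30. The schedule ends AE documentation at a prompt end-of-treatment entry, and 6.4.4 treats discontinuation of Afinitor as a reason to end documentation. For patients who stop at progression, ascertainment in days 1–30 is passive throughout; for those in PFS follow-up it is passive for unrelated AEs.

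The window is at most about 9% of the AE period, if all 3000 patients contribute it in full and the 10-month average is time on treatment. AEs in it may be incompletely ascertained. Whether they are, and by how much, cannot be derived from the documents; the range from 0% to 16.5% of events missed rests on assumed rates. This is an inexpensive improvement to safety ascertainment, not a flaw that undermines the study.

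**What to change.** - In 6.4, 6.4.4 and the scheme, state that AE entry continues to day 30 after the end of treatment in accordance with 7.1, and that ending documentation because of discontinuation does not close AE entry before then.
- Keep the prompt end-of-treatment entry, and add one separate eCRF item, 'AE and vital status to day 30'. It is completed from the patient record or the next routine contact, no earlier than day 30, for all patients who end treatment, including those who progressed.
- Have the first PFS follow-up entry also ask about AEs of any cause in days 1–30.

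No extra visit is needed, so the non-interventional design is unaffected. The cost is one short additional entry per patient, and some items will be missing; their number would at least show how completely the window was observed.

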7.2 Serious Adverse Events

- are fatal,
- are life-threatening¹,
- require or prolong hospitalisation,
- lead to inability to work, persistent or severe disability or incapacity³,
- result in a congenital anomaly or birth defect,
- are medically significant⁴.

1 Refers to an adverse event that carries a fatal risk for the patient at the time of the reaction. It does not refer to a reaction that could hypothetically result in death if it developed to a higher level of severity or complications.

2 This refers to inability to work as a result of permanent damage to health

3 Disability is considerable incapacity or permanent damage

4 Medically significant adverse events (AEs) are AEs that are not immediately fatal or life threatening or necessitate hospitalisation, but can considerably impair the patient. AEs are also medically significant if they require intervention/treatment to prevent a condition corresponding to the criteria for the definition of an SAE.

Inpatient treatment is not considered to be a serious adverse event if one of the following points applies:

a) Hospitalisation, that is part of the standard of care or surveillance of the disease investigated in the NIS and that is not due to worsening of the disease

- b) Elective admission or hospitalisation, that was already planned before inclusion in the NIS for the treatment of pre-existing diseases without relation to the disease investigated in the NIS and without deterioration since application of the drugs studied in this NIS
- c) Hospitalisation for social reasons and for short-term care without deterioration of the patient's general condition or the disease investigated in this study.

The decision as to whether an event constitutes an SAE depends only on whether one of the formal criteria named above is present and is *independent of the assessment of whether there is a causal relationship between taking a drug and the occurrence of the SAE*.

Reporting periods for SAEs

All serious adverse events are to be documented fully in the electronic case report form (eCRF) under the "Adverse Events" tab and submitted in the system within 24 hours of becoming known. Exception: In the event that entering an SAE in the eCRF is impossible for technical or other reasons, the SAE report can also be faxed as a hard copy "SAE report" directly to **Exception**.

If sent by fax, the date of the fax is to be written on the original report form, which remains in the study documentation in the study site.

If the information on the serious adverse event is provisional in nature, it should be finally completed as soon as possible and sent to Novartis within 24 hours after the **new information becomes known as an SAE follow-up**.

Recurring manifestations, complications or progression or deterioration of the initial SAE must be reported to Novartis as a follow-up to the original report within 24 hours of becoming known. An SAE assessed to be completely independent of a previously reported SAE should be reported as a new event.

